#### **RESEARCH DESIGN AND METHODS:**

**Study design:** Pre-post withdrawal quasi-experimental study using interrupted time series analysis.

**Study sites:** Six inpatient medical units within Vanderbilt University Hospital will serve as study units. These have been selected due to a higher rate of HO-MDRO/*C. difficile* incidence and/or a higher proportion of admissions comprising LCTF patients. The proposed acute care units have an average of 4,952 patient days per month with LTCF residents comprising 4.3-5.6% of unit admissions. This percentage is likely an underestimation because not all places of patient origin are documented and transfers between units within VUH are not included in this analysis. The HO-MDRO/*C. difficile* rate of these 6 units combined was 4.62 per 1,000 patient days for 2014.

**Study procedures:** After a 6 month baseline period, all units will be transitioned to a 6 month intervention period where all patients transferred onto the study units with LTCF origin prior to admission will be placed on preemptive Contact Precautions (Figure 5). Both patients admitted directly to a study unit as well as patients transferred from a non-study unit onto a study unit will be included under the policy. A washout period of 2 weeks will be introduced before a post-intervention withdrawal period of 6 months is implemented.

Inclusion/exclusion criteria: All patients admitted to the unit will be included in the study. There will be no exclusion criteria.

**Primary outcome - Rate of hospital-onset MDRO and** *C. difficile* **infections:** Aggregate rates of all hospital-onset (HO)-MDRO infections (Table 3), including MRSA, *C. difficile*, VRE, ESBL+ GNB, CRE, and MDR *Acinetobacter*, on participating units will be calculated. As active surveillance for these pathogens is not performed at VUH, only culture specimens obtained for clinical decision making will be included. Specimens from any site (e.g. blood, urine, wound) will be included. These events will be captured daily using the Vanderbilt Infection Prevention Electronic Resource (VIPER), an HAI surveillance platform that monitors laboratory results in real time. Events will be classified as HO if the specimen was collected >3 days after admission to VUH (i.e. on or after day 4).

Secondary outcomes:

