ESBL + GNB (extended-spectrum beta-lactamase producing gram- negative bacillus)	Any E. coli , K. pneumoniae and K. oxytoca demonstrated to have ESBL activity based on results from BD Phoenix through microdilution methodology. The BD Phoenix performs ESBL testing using cephalosporins (ceftazidime/cefotaxime/ceftriaxone) + clavulanic acid.

Table 3:	Definitions	of MDROs	Included in	Primar	y Study	y Outcome
----------	-------------	----------	-------------	--------	---------	-----------

2) Subgroup examinations of individual pathogen HO-infection rates for the overall study population and the aggregate HO-MDRO/*C. difficile* infection rate for each individual study unit

**Covariates:** Several factors may affect the impact of the intervention on the primary outcome. These will be measured and included in the analysis.

**1) Hand hygiene compliance:** Study unit compliance with hand hygiene as monitored by the Vanderbilt Hand Hygiene Program^34 will be included for analysis.

2) PPE compliance: Trained study personnel will perform audits of PPE use by HCP caring for patients placed into the preemptive intervention.

**3) Antimicrobial utilization:** Use of broad-spectrum antibiotics is currently tracked as a part of the VUMC Antibiotic Stewardship Program (Co-directed by Epicenter investigator [name]). Because antibiotic use is a factor in the acquisition of MDROs and *C. difficile*, we will include a measure of broad-spectrum antimicrobial use in the analysis (measured as days of therapy [DOT]).

**Analysis:** The rates of the primary and secondary outcomes will be compared for the following phases, defined *a priori*: 6 month baseline period, 6 month intervention period, and 6 month withdrawal period. In addition, a more robust interrupted time-series regression analysis with Newey-West standard errors will be performed using bimonthly outcome rates (which will provide 12 separate time point measurements for each period).

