**Sample size considerations:** Existing data were used to assess sample size adequacy. Using patient-days, the mean patient days per period will be 4,952 patient days/month for a total of 29,710/period. The rate of HO-MDROs on the units of interest is 4.6/1000 patient days for an average of 137 evaluable events per period. This study will have 80% power to detect a true difference in infection rates of 1.4/1000 patient days. That means a reduction by approximately 42 events in the intervention period. Nursing home admissions (those that will receive the intervention) are at least 4.3-5.6% on target units which is likely an underestimate given the current reporting system.

**Safety:** A data safety monitoring board (DSMB) will be created to oversee any potential adverse events that would require further assessment and intervention. At present 100% of falls, including all falls with harm, have an event review as part of the VUH quality program. The current fall rate on the four proposed units is 2.6 falls/month. The DSMB will review the event analysis of all falls on the unit on a quarterly basis with more in depth interim analysis of all falls stratified by study intervention. Due to the low rates of baseline falls, there is the potential for low case counts to cause large percentage increases, making a pre-defined threshold difficult for stopping the trial. If a sustained, significant increase in falls is seen and thought to be due to the Contact Precautions intervention, then the study will be halted.

**Limitations and future directions:** The evaluation of preemptive Contact Precautions for patients with LTCF exposure will be conducted in an academic, tertiary referral hospital with high rates of hand hygiene compliance. Preemptive isolation is a supplementary strategy and may not be generalizable to acute care hospitals with suboptimal hand hygiene compliance. If an impact on HO infections is seen during the intervention without unintended consequences, then there may be other high risk epidemiologic groups that could benefit from preemptive isolation. If this trial shows a reduction in HO-MDRO rates, this strategy may benefit from a larger-multicenter trial with randomization. This study has the potential to transform how isolation policies are implemented in acute care hospitals and could reduce the risk of pathogen transmission to other HCP and their patients.

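### Aim III's stated 80% power matches a calculation with independent (Poisson) events and no allowance for extra variation, so it is optimistic for the simple phase comparison of transmissible infections

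*Protocol*

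**What the plan says.** All references are to the protocol, Specific Aim III.

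- **Sample size considerations.** Exposure is pooled over the six units: "the mean patient days per period will be 4,952 patient days/month for a total of 29,710/period". Events follow from one aggregate rate: "The rate of HO-MDROs on the units of interest is 4.6/1000 patient days for an average of 137 evaluable events per period". The claim is "This study will have 80% power to detect a true difference in infection rates of 1.4/1000 patient days", and the next sentence translates it: "That means a reduction by approximately 42 events in the intervention period". The paragraph gives no alpha, sidedness, test or dispersion.
- **Study sites.** The baseline rate comes from existing data: "The HO-MDRO/*C. difficile* rate of these 6 units combined was 4.62 per 1,000 patient days for 2014".
- **Study procedures and Primary outcome.** All six units move from baseline to intervention to withdrawal at the same time. Clinical cultures from any body site count, and the paragraph states no limit of one event per patient.
- **Analysis.** "The rates of the primary and secondary outcomes will be compared for the following phases", namely "6 month baseline period, 6 month intervention period, and 6 month withdrawal period". The test is not named. An interrupted time series with Newey-West standard errors, 12 points per period, is planned in addition.

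**The concern.** Pooling all patient-days into one rate and sizing on the event count alone treats each infection as unrelated to every other. The Aim III rationale says the opposite: patients from long-term care are described as a source from which these organisms spread to others, and the isolation policy is meant to interrupt that spread. If one case raises the risk of another, counts vary more than a Poisson count does. Several positive specimens from one patient would add to this if they are counted separately. So would any hospital-wide change in the rate from one half-year to the next, because all units switch together and such a change does not average out over units.

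The 80% is the only operating characteristic given for Aim III. If it is a best case, a true fall of 1.4/1000 could be missed more often than readers expect, and a null result could be over-read as evidence against preemptive isolation.

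**Working it through.** **Inputs from the protocol.** Exposure T = 29.71 thousand patient-days per period (4,952 × 6 = 29,712, a rounding difference). Baseline rate 4.6/1000; difference 1.4/1000, hence 3.2/1000 under intervention. Assumed because not stated: two-sided 5%.

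**Reproducing the plan's figure.**

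- Events: 4.6 × 29.71 = 136.7 (protocol: 137) and 3.2 × 29.71 = 95.1. The reduction is 1.4 × 29.71 = 41.6 (protocol: about 42).
- Standard error of the rate difference with Poisson variance: √[(4.6 + 3.2)/29.71] = 0.512 per 1000.
- z = 1.4/0.512 = 2.73. Power = Φ(2.73 − 1.96) = 78.0%.
- A two-proportion calculation gives 78.2%, the square-root transform 78.3% and the log rate ratio 77.6%.
- Power reaches 80% at 1.43/1000, which rounds to the protocol's 1.4.

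The stated figure is therefore what independent events give at two-sided 5%, with nothing in reserve.

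**Adding extra-Poisson variation.** Let the count variance be φ times the mean, and let the test allow for it. Then power = Φ(2.73/√φ − 1.96). The detectable difference d at 80% power solves d = (1.96 + 0.84) × √[φ(9.2 − d)/29.71]. If the test keeps the Poisson variance instead, its true two-sided error is 2[1 − Φ(1.96/√φ)]. The values of φ are assumptions; the documents give none.

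| φ (assumed) | Power at 1.4/1000, valid test | Detectable difference, 80% power | Type I error if Poisson variance is kept (nominal 5%) |
|---|---|---|---|
| 1.0 | 78% | 1.43 | 5% |
| 1.2 | 70% | 1.6 | 7% |
| 1.5 | 61% | 1.7 | 11% |
| 2.0 | 49% | 2.0 | 17% |
| 3.0 | 35% | 2.3 | 26% |

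**How little variation is needed.** Suppose the true overall rate varies between periods with coefficient of variation k. The variance of the difference in counts is then 136.7 + 95.1 + k²(136.7² + 95.1²).

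- k = 5%: variance 301 against 231.7, so φ is about 1.3 and power 67%.
- k = 10%: variance 509, so φ is about 2.2 and power 45%.

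These k values are also illustrations.

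**The case against.** **A reader might infer that the 80% can arise only from independent events.** The documents do not settle this, because alpha and sidedness are absent. At one-sided 5%, independent events give 86%, and φ of about 1.2 gives 80% (z = 2.73/√1.2 = 2.49; Φ(2.49 − 1.645) = 80%). A modest allowance under a one-sided test therefore cannot be excluded, although the paragraph mentions neither.

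**A reader might also infer that the false-positive rate is higher than stated.** No false-positive rate is stated for Aim III, and the phase test is not named. The last column of the table applies only if that test keeps Poisson variance. Naming the test may properly be left to a statistical analysis plan.

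**Six units do not in themselves cost power.** The same units appear in every phase, so stable differences between them cancel. Only unit-by-period variation, outbreaks, repeat events and drift remain. Nor need every hospital-onset event be an in-unit transmission: the Aim III Significance section cites 45.6% MDRO colonization at baseline in one long-term care cohort.

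**The plan has a partial safeguard.** The time series with Newey-West errors addresses serial correlation and does not impose Poisson variance, and hand hygiene, PPE compliance and antimicrobial use are to enter the analysis.

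All of this stands and limits the point. It does not remove it: the time series is an addition to the phase comparison, and the power statement is not tied to it. The claim at issue is a number the protocol itself gives, so it is not a detail awaiting a later document.

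**Conclusion.** The concern holds in a limited form. The arithmetic in the protocol is sound, but the 80% at 1.4/1000 corresponds to independent events at an assumed two-sided 5%, with no visible allowance for the dependence that the study's own rationale implies. For the simple phase comparison it should be read as a best case.

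The size of the loss cannot be fixed from the documents. Under an assumed variance inflation of 1.2 to 3, power falls to between about 70% and 35%, and the detectable difference rises to between about 1.6 and 2.3 per 1000. A higher false-positive rate is conditional on a phase test that keeps Poisson variance, which the protocol neither states nor excludes.

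**What to change.** 1. Estimate the dispersion, and the month-to-month correlation, from the unit-by-month counts behind the 2014 rate. The protocol reports only the combined rate; it is assumed here that the counts can be retrieved from the existing surveillance data.
2. In Sample size considerations, state alpha and sidedness, and restate the power or the detectable difference with the estimated inflation. For example, the detectable difference would be about 1.7/1000 at φ = 1.5 and about 2.0/1000 at φ = 2.
3. In Analysis, make the phase comparison one that allows overdispersion. One suitable form is a log-linear count model with a patient-day offset, unit and phase effects, and quasi-Poisson or negative binomial variance. Its variance should also reflect any period-to-period drift found in step 1, since all units switch together.

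The cost is one recalculation and a few sentences of protocol text. The stated detectable difference becomes less favourable. No extra patients or data collection are needed.

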#### Information Applicable to All Vanderbilt Epicenter Study Aims:

Regulatory Plans: Each individual research Aim project will be submitted to the Vanderbilt Institutional Review Board (IRB) for review prior to study onset. Vanderbilt has also developed IRBshare, a joint IRB review model for multisite studies that provides a mechanism to streamline IRB submission and the IRB review process at all phases of IRB review through the sharing of and reliance on IRB-approved documents between IRBs. This will be available for Vanderbilt Epicenter investigators for any multisite Epicenter research project. Volunteers for Aim I will undergo informed consent prior to study participation, although it is anticipated that the risks to subjects from participation in the simulation experiments will be minimal. For the Aim II audit and performance feedback project, we will request exemption from informed consent due to the minimal risk of observed subjects and the impact of obtaining informed consent on the validity of the observation data. Observers will be trained to note when significant breaches in PPE use occur that would warrant additional intervention above routine infection prevention practices such as hand hygiene. We will also request exemption from informed consent for study Aim III. Similar to the study of universal gown and glove use in the ICU (BUGG study), this aim evaluates different infection prevention isolation policies. The BUGG study finding of no difference in adverse events among intervention subjects is reassuring regarding minimal

risk. We will have as an added measure, a formal safety monitoring group to investigate any increases in patient fall events among study subjects as a matter of added assurance.

**Evaluation Plan:** Several processes will be used to evaluate the Vanderbilt Epicenter program to ensure a research program that is innovative and up-to-date. Investigators will stay abreast of emerging issues and knowledge gaps related to the prevention of infectious pathogen transmission in healthcare settings through regular assessment of the medical literature and attendance at major scientific meetings in the field (i.e. IDWeek, SHEA Spring Scientific meeting). Vanderbilt Epicenter project findings will be submitted for publication in peer-review journals to disseminate this information to the healthcare epidemiology audience. Using the Advisory and Steering Committee, which will meet quarterly, the progress on the research plan in accordance to the timeline below will be tracked. Additional metrics will include the number of abstract presentations at scientific meetings, study-related publications, and creation of new study protocols in response to identified evidence gaps and CDC requests.

		Year 1		Year 2				Year 3				
Quarter	1	2	3	4	1	2	3	4	1	2	3	4
Aim I												
Scenario development/planning												
Subject recruitment												
Experiments in simulation center												
Data analysis												
Presentation and publication of findings												
Aim II												
Audit tool development												
Observer training, study unit selection												
Baseline observation period												
Awareness/accountability period												
Data analysis												
Presentation and publication of findings												
Aim III												
Finalize study protocol/implementation												
Baseline period												
Intervention period												
Withdrawal period												
Data analysis												
Presentation and publication of findings												

#### Timeline for Vanderbilt Epicenter Research Plan:

**Translation of Epicenter Findings/Future Directions:** Successful completion of the Vanderbilt Epicenter projects will advance the understanding of various aspects of transmission-based precautions used to prevent pathogen spread in healthcare settings. This includes the development of tools to audit and train HCP on the appropriate and safe use of PPE, methods to hardwire such practices, novel strategies to evaluate new protocols (i.e. using simulation tools), and alternative strategies for use of these precautions. These results may direct future guidelines and policies surrounding safe use of PPE and should stimulate future hypothesis-generation for additional studies on these important issues.

